12.9 Handling and Reporting of Adverse Events

An adverse event is any untoward medical occurrence (including a symptom or disease or an abnormal laboratory finding) during treatment with an investigational drug or a pharmaceutical product in a subject that does not necessarily have a relationship with the treatment being given.

*Abnormalities based on laboratory parameters, vital signs, and 12-Lead ECG will be called AE, if they are associated with at least one of the following:

- Interruption or stoppage of the study medication
- Associated with signs or symptoms
- Requiring treatment
- Considered clinically significant by the investigator

Safety Criteria:

An independent, unblinded study physician (from CRO) will assess each cohort for safety. A cohort will be declared safe as soon as all results are available for the Day 15 visit if the following conditions are met:

- No toxic deaths (deaths judged by the investigator to be related to either study drug);
- Not more than 1 toxic SAE (SAEs judged by the investigator to be related to either study drug);
- No Grade 3 or higher toxicities (including laboratory AEs as per CTCAE version 5.0 or higher) (AEs judged by the investigator to be related to either study drug);
- <4 subjects with any grade toxicity (AEs judged by the investigator to be related to either study drug).

In addition to the cohort-level safety, the independent study physician (from CRO) will determine if any subjects meet Individual Stopping Criteria:

- Subjects who develop a Grade 3 toxicity that is assessed by the investigator to be related to the study drug are to be permanently discontinued from study treatment but will continue in the study for safety assessments.
- Subjects who develop a Grade 4 toxicity, regardless of relatedness to study drug, are to be permanently discontinued from study treatment but will continue in the study for safety assessments.

In addition to the individual subject-level safety, the independent study physician (from CRO) will determine if a cohort meets Cohort-level Stopping Criteria prior to completing the 16 subjects, in which case no additional subjects will be enrolled into that cohort and no higher brequinar doses will be assessed:

Protocol for clinical study of Brequinar

Protocol No.: 21-VIN-0372

Version No.: 2.1; Dated: 29 Dec 2021

Supersedes: 02; Date of Supersedes: 30 Sep 2021

- ≥ 3 brequinar-treated or combination-treated subjects meet the individual stopping criteria.
- ≥ 5 brequinar-treated or combination-treated subjects develop a Grade 3 or higher AE regardless of relationship to study drug.

Adverse Drug Reaction is a noxious and unintended response to a medicinal product related to any dose. The phrase responses to a medicinal product means that a causal relationship between a medicinal product and an adverse event is at least a reasonable possibility, i.e. the relationship cannot be ruled out. Regarding marketed medicinal products: a response to a drug which is noxious and unintended and which occurs at doses normally used in man for prophylaxis, diagnosis, or therapy of diseases or for modification of physiological function.

An **Unexpected Adverse Drug Reaction (UADR)** is an adverse reaction, the nature or severity of which is not consistent with the applicable product information [e.g., investigator's brochure for an unapproved investigational medicinal product or company core data sheet or package insert for marketed product].

Subjects will be monitored throughout the study period for adverse events. Subjects will be instructed to bring to the notice of study personnel any adverse event that may occur during the entire study period.

The following information is to be recorded for each adverse event individually in Adverse Event Reporting Form.

- Type of adverse event*
- Is it serious or non-serious?
- Date of onset/reporting
- Date of onset and resolution
- Severity (as per section 12.12)
- Association with the study medication (as per section 12.13)
- Action taken
- Outcome of adverse event (as per section 12.14)
- Further details of the AE, if any.

*The investigator should attempt to establish a diagnosis of the event based on signs, symptoms, and/or other clinical information. In such cases, the diagnosis should be documented as the AE/SAE and not the individual signs/symptoms.

For the recording of signs and symptoms, the subject will be required to report spontaneously any AEs as well as the intensity of these events. In addition, each subject will be asked by the investigator for AEs during vital

Protocol for clinical study of Brequinar

Protocol No.: 21-VIN-0372

Version No.: 2.1; Dated: 29 Dec 2021

Supersedes: 02; Date of Supersedes: 30 Sep 2021

signs and physical examination. All AEs including both observed and volunteered ones will be recorded in the Adverse Event Reporting Form, irrespective of its association with study medications. All findings considered clinically relevant and reportable as AE by investigator will be reported on the “Adverse event” page in the CRF and in the subject's medical records.

Each AE will be evaluated for duration, severity and action taken, outcome and association with study medication.

Adverse events/ Serious Adverse Events will be recorded from signing informed consent form through the end of the study safety assessments. Other medical events not related to study screening occurring before first dose administration, but after signing the informed consent form will be recorded on the medical history/current medical conditions of case report form.

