Quantitative PCR (qPCR)	
Obtain a NP/OP swab sample to be processed as outlined in the laboratory manual and sent to a central lab for analysis of quantitative PCR.

Protocol for clinical study of Brequinar

Protocol No.: 21-VIN-0372

Version No.: 2.1; Dated: 29 Dec 2021

Supersedes: 02; Date of Supersedes: 30 Sep 2021

Drug Analysis:	Plasma concentration of brequinar and dipyridamole will be quantified at the Bioanalytical facility of Veeda Clinical Research Ltd.
Safety Criteria:	
An independent, unblinded study physician (from CRO) will assess each cohort for safety. A cohort will be declared safe as soon as all results are available for the Day 15 visit if the following conditions are met:
 
 • No toxic deaths (deaths judged by the investigator to be related to either study drug); • Not more than 1 toxic SAE (SAEs judged by the investigator to be related to either study drug); • No Grade 3 or higher toxicities (including laboratory AEs as per CTCAE version 5.0 or higher) (AEs judged by the investigator to be related to either study drug); • <4 subjects with any grade toxicity (AEs judged by the investigator to be related to either study drug). 
In addition to the cohort-level safety, the independent study physician (from CRO) will determine if any subjects meet Individual Stopping Criteria:
 
 • Subjects who develop a Grade 3 toxicity that is assessed by the investigator to be related to the study drug are to be permanently discontinued from study treatment but will continue in the study for safety assessments. • Subjects who develop a Grade 4 toxicity, regardless of relatedness to study drug, are to be permanently discontinued from study treatment but will continue in the study for safety assessments. 
In addition to the individual subject-level safety, the independent study physician (from CRO) will determine if a cohort meets Cohort-level Stopping Criteria prior to completing the 16 subjects, in which case no additional subjects will be enrolled into that cohort and no higher brequinar doses will be assessed:
 
 • ≥ 3 brequinar-treated or combination-treated subjects meet the individual stopping criteria; • ≥ 5 brequinar-treated or combination-treated subjects develop a Grade 3 or higher AE regardless of relationship to study drug.

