9.0 STUDY PROCEDURE

9.1 Study Design

The first part of the study will be a phase II, randomized, assessor-blind, multicenter, multi-dose, placebo-controlled study in approximately 64 subjects with mild to moderate COVID-19 infection confirmed by a positive SARS-CoV-2 RT-PCR qualitative test /rapid antigen test and who have at least mild to moderate signs and/or symptoms ongoing at study entry.

Approximately 32 subjects (50% of subjects per arm per cohort) at selected sites will be invited to participate in the “PK” arm of the study until approximately 8 subjects in each cohort have been recruited after providing written informed consent for the same. PK includes brequinar and dipyridamole plasma concentrations.

If a particular cohort meets study stopping criteria (as defined in section “Stopping Criteria”) or is found to be unsafe by DSMB members, then the study will not proceed with enrollment of subsequent cohorts.

An expansion cohort of approximately 48 subjects will be added to the cohort with the highest brequinar dose that meets safety criteria.

Safety data of cohort 1 to cohort 4 (or highest dose cohort evaluated) will be submitted to the regulators and their approval will be obtained prior to commencing recruitment in the expansion cohort.

All subjects will receive SOC as per relevant guidelines for treatment of patients with mild to moderate COVID-19 infection.

Subjects will be randomized to one of the following cohorts in Part 1:

Cohort 1:

- Arm 1: 5 days of standard of care (SOC) + brequinar 50 mg OD + dipyridamole 75 mg TID (N = 8)
- Arm 2: 5 days of SOC + brequinar 50 mg OD (N = 4).
- Arm 3: 5 days of SOC + brequinar placebo 50 mg OD (N = 4).

Cohort 2:

If the 50 mg brequinar OD + dipyridamole 75 mg TID meets safety criteria as pre-defined in the protocol the brequinar dose will be escalated to 100 mg.

- Arm 1: 5 days of standard of care (SOC) + brequinar 100 mg OD + dipyridamole 75 mg TID (N = 8)
- Arm 2: 5 days of SOC + brequinar 100 mg OD (N = 4).
- Arm 3: 5 days of SOC + brequinar placebo 100 mg OD (N = 4).

Cohort 3:

If the 100 mg brequinar OD + dipyridamole 75 mg TID meets safety criteria as pre-defined in the protocol the brequinar dose will be escalated to 150 mg:

Protocol for clinical study of Brequinar

Protocol No.: 21-VIN-0372

Version No.: 2.1; Dated: 29 Dec 2021

Supersedes: 02; Date of Supersedes: 30 Sep 2021

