9.6 Sample Size

No statistical powering has been performed for this study. The number of subjects is designed to provide information on the safety, tolerability, and efficacy of the IMP tested in this study. In Part 1, approximately 64 subjects will be randomized to up to 4 cohorts of 5 consecutive days of one of the following regimens in addition to SOC in 2:1:1 ratio as shown below:

Treatment Arm ^a	Day 1	Day 2	Day 3	Day 4	Day 5
Brequinar + Dipyridamole (N=8)	BRQ XX mg OD DPY 75 mg TID				
Brequinar (N=4)	BRQ XX mg OD				
Placebo (N=4)	PBO XX mg OD				

Protocol for clinical study of Brequinar

Protocol No.: 21-VIN-0372

Version No.: 2.1; Dated: 29 Dec 2021

Supersedes: 02; Date of Supersedes: 30 Sep 2021

^aAll subjects will also received standard of care (SOC).

The brequinar dose will start at 50 mg and may be escalated to 100 mg, 150 mg, and 200 mg if safety criteria are met for each cohort (see Safety Criteria below).

The hospital pharmacist is to be unblinded. Bulk supplies of investigational medicinal product (IMP) of brequinar 50 mg, brequinar 100 mg, dipyridamole 75 mg, brequinar placebo 50 mg and brequinar placebo 100 mg will be supplied to the unblinded hospital pharmacist.

The unblinded hospital pharmacist is to prepare the assigned IMP for each individual subject at that institution and create an appropriately labeled bottle/zip lock bag of study medication sufficient for a 5-day treatment course. The randomization assignment will be provided via an IWRS.

Alternatively, the hospital pharmacist and study team may decide to distribute IMP on a daily basis for 5 days for brequinar and dipyridamole while the subject is hospitalized, depending on the most convenient method.

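### The Day 15 escalation gate omits the any-cause cohort stopping criteria, so Section 12.9 can declare safe a full cohort that Section 9.1 bars from escalation

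*Combined protocol and SAP*

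**What the plan says.** All references are to protocol Version 2.1.

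**Stopping check.** Section 12.9 asks the independent CRO physician to determine whether "a cohort meets Cohort-level Stopping Criteria prior to completing the 16 subjects, in which case no additional subjects will be enrolled". The same sentence rules out higher brequinar doses. The synopsis Safety Criteria carry the same limit: "a cohort meets Cohort-level Stopping Criteria prior to completing the 16 subjects". There are two criteria: at least 3 active-treated subjects meeting the individual stopping criteria, or at least 5 where "brequinar-treated or combination-treated subjects develop a Grade 3 or higher AE regardless of relationship to study drug". The individual criteria cover related Grade 3 events, but for Grade 4 cause is irrelevant: "Subjects who develop a Grade 4 toxicity, regardless of relatedness to study drug, are to be permanently discontinued from study treatment".

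**Day 15 gate.** Section 12.9 also states: "A cohort will be declared safe as soon as all results are available for the Day 15 visit if the following conditions are met". The four conditions are no related deaths, at most one related SAE, no related Grade 3 or higher event, and fewer than four subjects with a related event of any grade. All four turn on the investigator's judgement of relatedness.

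**Consequence for dose.** Section 9.6 says the dose "may be escalated to 100 mg, 150 mg, and 200 mg if safety criteria are met for each cohort (see Safety Criteria below"). Section 9.1 likewise provides for escalation when the combination meets the safety criteria. But 9.1 also has a rule that opens "If a particular cohort meets study stopping criteria (as defined in section" and ends by barring later cohorts, with no time limit. It points to a section called Stopping Criteria; the synopsis version points to Safety Criteria. Section 9.2 convenes the DSMB and suspends enrolment if the cohort-level criteria are met, again with no time limit.

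**The concern.** Section 12.9 has a mid-cohort brake that includes any-cause events and an end-of-cohort gate that counts related events only. The brake's wording ends when the cohort is complete, and nothing carries its criteria into the gate. The same set of unrelated severe events can therefore forbid higher doses if seen early, yet leave the cohort declared safe if seen late. Late is not an odd case: the 16th subject's dosing and the Day 8 and Day 15 laboratory tests all follow the 16th enrolment.

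At stake is the dose-escalation decision for a combination that Section 5.5 says has not been tested clinically before. The same decision also picks the expansion dose. The any-cause criteria are the cohort rules that depend least on a relatedness call. The minimum DSMB schedule in Section 9.2 has no review between cohorts, so at each step the CRO physician works from this text, and it should give one answer.

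**Working it through.** **1. Cohort size.** Section 9.6 gives 8 + 4 + 4 = 16 per cohort, and 4 × 16 = 64, which agrees with the plan's total for Part 1. Active subjects per cohort: 8 combination + 4 brequinar = 12.

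**2. Which outcomes fall between the rules.** One related Grade 3 or higher event fails the Day 15 list, so only outcomes with all such events judged unrelated matter. Write (a, b) for the number of active subjects whose worst unrelated event is Grade 3 (a) or Grade 4 (b). A stopping criterion is met if b ≥ 3 or a + b ≥ 5. The smallest outcomes that meet a criterion yet pass the list are (0, 3), (3, 2), (4, 1) and (5, 0).

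**3. What each section does with a late (5, 0).**
- 12.9 stopping check: if completing means enrolment, the period has ended. If it means follow-up, the check still applies and most of the gap closes.
- 12.9 Day 15 list: passes.
- 9.1 stopping rule: no later cohorts, unless its reference to the definition brings in the 16-subject limit.
- 9.2: DSMB convened. It may let enrolment resume if safety criteria are met, without saying whether that means the four conditions or the whole block.

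**4. How often a criterion is met at any time.** P(X ≥ k) = Σ from j = k to 12 of C(12, j) p^j (1 − p)^(12 − j). Section 5.4 gives the outpatient study's Grade 3 counts: 1 of 56 on brequinar and 3 of 59 on placebo, so 4/115 overall, with no Grade 4 events. Other rates are confidence limits or assumptions, as marked.

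| Unrelated Grade 3 or higher, p | P(≥5 of 12) |
|---|---|
| 1/56 = 1.8% | 0.00013% |
| 4/115 = 3.5% | 0.003% |
| 8.7% (upper limit, two-sided 95%, 4/115) | 0.23% |
| 15% (assumed) | 2.4% |
| 20% (assumed) | 7.3% |

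| Unrelated Grade 4, p | P(≥3 of 12) |
|---|---|
| 2.6% (one-sided 95% upper limit, 0/115) | 0.3% |
| 5% (assumed) | 2.0% |
| 5.2% (one-sided 95% upper limit, 0/56) | 2.2% |
| 10% (assumed) | 11% |

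**5. How much of this falls after the 16th enrolment.** The documents give neither accrual pace nor onset times. I assumed 16 enrolments spread evenly at random over 14, 28 or 56 days, 12 of them active at random, and onset uniform over Days 1–8 or 1–15 (200,000 simulated cohorts per setting). Share of crossings that come after the 16th enrolment, and the product with step 4:
- ≥5 Grade 3 or higher at 15%: share 0.43–0.96, so 2.39% × share = 1.0–2.3% per cohort.
- ≥5 Grade 3 or higher at 20%: share 0.39–0.94, so 7.26% × share = 2.8–6.8%.
- ≥3 Grade 4 at 5%: share 0.27–0.85, so 1.96% × share = 0.5–1.7%.
- ≥3 Grade 4 at 10%: share 0.26–0.82, so 11.1% × share = 2.9–9.1%.

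The shares move by several points with the coding of enrolment and onset days. If Grade 4 onset is confined to the five dosing days, the Grade 4 shares are about 24–53%. The order of magnitude does not change.

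**The case against.** The strongest reply is that the protocol already handles late events. Section 9.1 bars later cohorts and Section 9.2 convenes the DSMB, neither with a time limit. The wrong label in 9.1 is a slip, since only one set of cohort-level stopping criteria exists. This stands against the stronger reading a reader might take from 12.9 alone, namely that the criteria are tested only during enrolment and nothing catches a later crossing. The documents do not support that. What remains is that 12.9, which the CRO physician applies, and the escalation sentences in 9.1 and 9.6 can be read as allowing the step that 9.1's stopping rule forbids.

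Second, the two rules have different jobs, and gating on related events is defensible in an acute infection. The Day 15 list is strict: one related Grade 3 or higher event fails it, and Section 12.13 counts a possible relationship as related. That stands, and it confines the point to events judged unlikely or not related. It does not explain why the same unrelated events should bar escalation on one day and not on a later one.

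Third, other safeguards operate. SAEs go to the regulator, sponsor and ethics committee within 24 hours where required. The study can be suspended or stopped, and before expansion the regulators see the Part 1 safety data and "their approval will be obtained prior to commencing recruitment in the expansion cohort". These are real, but discretionary or, for expansion approval, after the last dose step.

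Fourth, the material probabilities rest on assumed rates. That is correct and governs the severity.

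**Conclusion.** The point holds as an inconsistency between sections, for late events judged unrelated, on the reading that completing the 16 means enrolling them. The clause about enrolling no further subjects favours that reading but does not settle it. A reader might call this a plain contradiction, or infer that drug-related severe toxicity could slip through to a higher dose. Neither is supported: on the follow-up reading most of the gap closes, and related Grade 3 or higher events always fail the Day 15 list.

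At the outpatient rates the Grade 3 case is remote, 0.0001% to 0.003% per cohort. It reaches a few percent only at about 15–20% unrelated Grade 3 or higher, or 5–10% unrelated Grade 4, and the post-enrolment figures also assume accrual pace and onset timing. Higher rates than in the outpatient study are conceivable, because most of its patients had very mild disease and this trial also admits moderate disease. In the hospitalized study 4 of 23 subjects (17.4%) had SAEs, but that was a sicker group, SAEs are not the same as Grade 3 events, and three of the four were on standard care alone. The documents do not give the rate to expect here. No sample size, error rate or endpoint is affected. Severity is minor: a cheap improvement to a safety gate.

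**What to change.** In the Safety Criteria of Section 12.9 and the synopsis:
1. Add to the Day 15 declared-safe conditions that no cohort-level stopping criterion has been met.
2. Replace the 16-subject limit with a statement that the cohort-level criteria apply through the last subject's Day 15 data.

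Leave every threshold as it is. As housekeeping, correct the cross-reference in 9.1 to Safety Criteria. When drafting, check that 9.2's condition for resuming enrolment still reads as intended, since the declared-safe list will have changed.

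The cost is a few words in an amendment, with no added subjects, visits or data. The downside is that COVID-19 worsening judged unrelated could occasionally block a dose step, and the criteria count active arms only, with no placebo comparison. Per cohort the chance is at most 2.4% at 15% and 7.3% at 20% Grade 3 or higher, or 2.0% at 5% and 11% at 10% Grade 4. These are ceilings, because they include crossings before the cohort is full, which the existing rule already blocks.

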Study Design:	
The first part of the study will be a phase II, randomized, assessor-blind, multicenter, multi-dose, placebo-controlled study in approximately 64 subjects with mild to moderate COVID-19 infection confirmed by a positive SARS-CoV-2 RT-PCR qualitative test /rapid antigen test and who have at least mild to moderate signs and/or symptoms ongoing at study entry.
 
Approximately 32 subjects (50% of subjects per arm per cohort) at selected sites will be invited to participate in the “PK” arm of the study until approximately 8 subjects in each cohort have been recruited after providing written informed consent for the same. PK includes brequinar and dipyridamole plasma concentrations.
 
If a particular cohort meets study stopping criteria (as defined in section “Safety Criteria”) or is found to be unsafe by DSMB members, then the study will not proceed with enrollment of subsequent cohorts.
 
An expansion cohort of approximately 48 subjects will be added to the cohort with the highest brequinar dose that meets safety criteria.
 
Safety data of cohort 1 to cohort 4 (or highest dose cohort evaluated) will be submitted to the regulators and their approval will be obtained prior to commencing recruitment in the expansion cohort.
 
All subjects will receive SOC as per relevant guidelines for treatment of patients with mild to moderate COVID-19 infection.
 
Subjects will be randomized to one of the following cohorts in Part 1:
 
Cohort 1:
 
 Arm 1: 5 days of standard of care (SOC) + brequinar 50 mg OD + dipyridamole 75 mg TID (N = 8) Arm 2: 5 days of SOC + brequinar 50 mg OD (N = 4). Arm 3: 5 days of SOC + brequinar placebo 50 mg OD (N = 4). 
Cohort 2:
 
If the 50 mg brequinar OD + dipyridamole 75 mg TID meets safety criteria as pre-defined in the protocol the brequinar dose will be escalated to 100 mg.
 
 Arm 1: 5 days of standard of care (SOC) + brequinar 100 mg OD + dipyridamole 75 mg TID (N = 8) Arm 2: 5 days of SOC + brequinar 100 mg OD (N = 4). Arm 3: 5 days of SOC + brequinar placebo 100 mg OD (N = 4).

Protocol for clinical study of Brequinar

Protocol No.: 21-VIN-0372

Version No.: 2.1; Dated: 29 Dec 2021

Supersedes: 02; Date of Supersedes: 30 Sep 2021

Cohort 3:

If the 100 mg brequinar OD + dipyridamole 75 mg TID meets safety criteria as pre-defined in the protocol the brequinar dose will be escalated to 150 mg:

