	
arrangements made for sample collection at the subject's home or other appropriate location.
 
 • Site staff (in case of an in-person visit) or subjects (in case of a remote visit) will assess respiratory rate, heart rate, body temperature and SpO₂ (a thermometer and pulse oximeter are to be provided to subjects who are home quarantined, leave the hospital or are unable to return for study visits). • Subjects will record details of concomitant medications, adverse events in the patient diary card (PDC). • Subjects will complete a symptom assessment form on designated days during the study period (days 1 – 8, 12, 15, 22, and 29). • In case the subject is hospitalized during the course of study, the activities specified in scheduled visits / time points will be carried out within the hospital facility. • Study completion or the reason for study discontinuation will be recorded in the source document and the eCRF. 
DSMB Meeting:
 
A Data Safety Monitoring Board (DSMB) will meet to review the safety and scientific conduct of the study. At a minimum, the DSMB will review the protocol and study design prior to study start, after the end of the first part of the study prior to the expansion phase, and at the end of the study.
 
At each interim meeting the DSMB members will determine whether to stop the study, amend the protocol, or continue the study per protocol. The study enrollment will not be suspended for routine DSMB meetings.
 
The DSMB will be convened and enrollment suspended if Cohort-Level Stopping Criteria are met. The DSMB may allow the enrollment to resume following their review if safety criteria are met.

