- Days 1, 8, 15 and 29 require sample collection for performing laboratory tests and will be conducted at the site or via home visit.
- Any in-person visit may also have telemedicine or telephone components if all study activities cannot be completed in person.
- The visits that include bloodwork must be conducted at the study site or arrangements made for sample collection at the subject's home or other appropriate location.
- Site staff (in case of an in-person visit) or subjects (in case of a remote visit) will assess respiratory rate, heart rate, body temperature and SpO₂ (a thermometer and pulse oximeter are to be provided to subjects who are home quarantined, leave the hospital or are unable to return for study visits).
- Subjects will record details of concomitant medications, adverse events in the patient diary card (PDC).
- Subjects will complete a symptom assessment form on designated days daily during the study period (days 1 – 8, 12, 15, 22, and 29).
- In case the subject is hospitalized during the course of study, the activities specified in scheduled visits / time points will be carried out within the hospital facility.
- Study completion or the reason for study discontinuation will be recorded in the source document and the eCRF.

DSMB Meeting:

A Data Safety Monitoring Board (DSMB) will meet to review the safety and scientific conduct of the study. At a minimum, the DSMB will review the protocol and study design prior to study start, after the end of the first part of the study prior to the expansion phase, and at the end of the study.

Protocol for clinical study of Brequinar

Protocol No.: 21-VIN-0372

Version No.: 2.1; Dated: 29 Dec 2021

Supersedes: 02; Date of Supersedes: 30 Sep 2021

At each interim meeting the DSMB members will determine whether to stop the study, amend the protocol, or continue the study per protocol. The study enrollment will not be suspended for routine DSMB meetings.

The DSMB will be convened and enrollment suspended if Cohort-Level Stopping Criteria are met. The DSMB may allow the enrollment to resume following their review if safety criteria are met.

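### The cohort stopping counts are written for the first 16 subjects of a cohort, so no stated count or denominator covers the 48-subject expansion, and what follows from a met criterion is worded in two ways

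*Combined protocol and SAP*

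**What the plan says.** All references are to protocol Version 2.1 (29 Dec 2021).

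- **The counts.** Section 12.9 (repeated in the 3.1 Safety Criteria) has an unblinded CRO physician decide whether "a cohort meets Cohort-level Stopping Criteria prior to completing the 16 subjects". The counts are 3 or more active-treated subjects meeting the individual stopping criteria (related Grade 3, or any Grade 4), or 5 or more with a Grade 3+ adverse event of any cause. If either is met, "in which case no additional subjects will be enrolled into that cohort and no higher brequinar doses will be assessed".
- **The expansion.** Section 9.1 adds about 48 subjects, 32 on the combination and 16 on brequinar alone, to the cohort at the highest dose that passed. Safety data go to the regulators first, and "their approval will be obtained prior to commencing recruitment in the expansion cohort".
- **The DSMB.** Sections 3.1 and 9.2 say "The DSMB will be convened and enrollment suspended if Cohort-Level Stopping Criteria are met", and then "The DSMB may allow the enrollment to resume following their review if safety criteria are met". The meeting schedule opens "At a minimum, the DSMB will review the protocol and study design prior to study start". The other two listed reviews fall between Part 1 and the expansion, and at study end.
- **The design text.** Sections 3.1 and 9.1 say that if a cohort meets the stopping criteria or the DSMB finds it unsafe, "then the study will not proceed with enrollment of subsequent cohorts".

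**The concern.** The primary objective is safety, and section 5.5 states that the two drugs have not been given together clinically before. Most exposure at the selected dose comes in the expansion, after the period for which the counts are worded. Someone running the expansion has to choose between having no count and carrying over a count designed for 12 active subjects, and the protocol does not choose for them. No DSMB review is scheduled while those 48 subjects are being dosed.

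A second, smaller uncertainty concerns what follows once a criterion is met. Section 12.9 closes the cohort and ends escalation. Section 9.2 describes a suspension that the DSMB may lift. No sentence says how the two fit together, and 9.2 does not mention whether escalation may restart.

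**Working it through.** **Inputs.** Each Part 1 cohort has 8 + 4 + 4 = 16 subjects, 12 of them active (section 9.6). Four cohorts give 4 × 16 = 64, which matches the stated size. The expansion has 32 + 16 = 48, all active (section 9.1). The study is unpowered (section 9.6), and no operating characteristics are given for the counts, so there is no plan figure for them to reproduce.

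**Exposure outside the counts.** Active subjects at the selected dose: 12 + 48 = 60, of whom 48/60 = 80% enter in the expansion. On the combination: 8 + 32 = 40, of whom 32 enter in the expansion.

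**Assumed rates.** The documents give no individual-stop rate for the combination. In the earlier outpatient study (section 5.4), related events on brequinar alone were all Grade 1 and there was no Grade 4. That is 0/56 stops, with an upper one-sided 95% limit of 1 − 0.05^(1/56) = 5.2%. I use 5% as a benign rate. The 10% and 20% rates are assumptions.

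**If the counts are carried over unchanged.** P(X ≥ k), X ~ Binomial(n, p):

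| True rate | ≥3 of 12 | ≥3 of 48 | ≥5 of 12 | ≥5 of 48 |
|---|---|---|---|---|
| 5% | 2.0% | 43.3% | 0.02% | 9.1% |
| 10% | 11.1% | 87.1% | 0.4% | 53.1% |
| 20% | 44.2% | 99.8% | 7.3% | 97.5% |

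A count of 3 is 3/12 = 25% of a Part 1 cohort's active subjects but 3/48 = 6.3% of the expansion. Read across unchanged, it becomes a different rule.

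**What the Part 1 gate already screens out.** A cohort is declared safe only with no related Grade 3+ toxicity (section 12.9). If every individual stop is a related event, a dose passes that criterion with probability (1 − p)^12: 0.95^12 = 54%, 0.90^12 = 28%, 0.80^12 = 7%. With 20% on the combination and 5% on monotherapy it is 0.80^8 × 0.95^4 = 14%. Unrelated Grade 4 events would not be screened by this criterion.

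**What a clean Part 1 leaves open.** Upper one-sided 95% limits: 0/12 gives 1 − 0.05^(1/12) = 22%, and 0/8 on the combination gives 1 − 0.05^(1/8) = 31%.

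**What a stated trigger could do.** Exact calculation, checking after every subject, with no reporting lag:

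| True rate | Combination arm: ≥3 of first 12, ≥4 of 20, ≥5 of 32 | Mean combination subjects dosed, of 32 | Scaled count, all active: ≥3/12, 6/24, 9/36, 12/48 |
|---|---|---|---|
| 5% | 3.8% | 31.4 | 2.0% |
| 10% | 26.1% | 28.3 | 12.0% |
| 20% | 82.2% | 18.1 | 56.8% |

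Scheduled laboratory tests after dosing fall on Days 8, 15 and 29 (section 9.11), so results lag enrolment. If 12 more subjects enrol before the deciding event is known (an assumption; 200,000 simulated trials), the combination-arm rule pauses before all 48 are dosed with probability 3%, 18% and 65%.

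**Gate and trigger together.** Multiplying the pass and pause probabilities, on the same all-related assumption, gives the chance that a dose passes Part 1 and is later paused: 0.540 × 0.038 = 2%, 0.282 × 0.261 = 7%, 0.069 × 0.822 = 6%.

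**The two consequences side by side.** Section 12.9 acts on the cohort and on higher doses. Section 9.2 acts on enrolment without naming a cohort.

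- If 9.2 means study enrolment, both can hold: the cohort closes, escalation ends, and the DSMB may restart enrolment elsewhere, for example into an expansion at a lower dose that passed.
- If 9.2 means the same cohort, its resume condition matters. Section 9.6 allows escalation "if safety criteria are met for each cohort (see Safety Criteria below", which points to the 12.9 list. Under that list any related Grade 3+ toxicity already bars resumption. The texts then conflict only when no triggering event is a related Grade 3+ toxicity, such as three unrelated Grade 4 events or five unrelated Grade 3+ events. The list is also judged on Day 15 results, which a part-filled cohort does not yet have.

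**The case against.** The expansion is not unsupervised. Individual stopping continues. Serious events go to the regulator, the sponsor/CRO and the ethics committee within 24 hours. The DSMB schedule is a minimum, so extra meetings are possible. The DSMB sentence carries no 16-subject limit, and 12.9 has the unblinded physician assess each cohort. Regulators must approve the expansion, and the study can be halted at any time. The Part 1 gate would usually reject a dose with a true 20% related-event rate, so the 82% pause figure describes a dose seldom expanded. At 10%, where the gate protects less, the example trigger pauses only about a quarter of the time.

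All of this stands, and it limits the practical gain. It does not supply a threshold or a denominator: none of these safeguards says how many events among the 48 should pause enrolment.

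Two stronger readings are tempting. A reader might infer that the protocol flatly contradicts itself, closing the cohort in one place and reopening it in another. Section 9.2 never says that the closed cohort may reopen, and its preceding paragraph speaks of study enrolment, so the contradiction is only one possible reading. The design text in 9.1 is not a third rival rule either, since barring later cohorts is compatible with 12.9. A reader might also infer that the expansion has no safety stopping at all, which the safeguards above contradict.

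**Conclusion.** The main point holds: the cohort counts are worded for the first 16 subjects, and the text does not say what becomes of them for the 48 expansion subjects, who make up 80% of active exposure at the selected dose. Neither default is satisfactory. Dropping the counts leaves no numerical enrolment trigger, and keeping a flat 3 gives a 43% chance of tripping at a 5% rate. A clean Part 1 does not settle the matter, because 0/8 on the combination is compatible with a rate of up to 31%.

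The secondary point holds only as an ambiguity. It disappears if 9.2 means study enrolment, and otherwise it is confined to triggers without a related Grade 3+ event.

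The exposure counts are arithmetic on stated numbers. The probabilities rest on assumed rates of 5%, 10% and 20%, the gate figures on all stops being related events, and the lag figures on an assumed 12 further enrolments. This should be fixed before the expansion opens.

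**What to change.** (a) In 12.9, state a trigger for the expansion that suspends enrolment and convenes the DSMB, with its denominator. One option is combination-arm individual stops of at least 3 of the first 12, 4 of the first 20, or 5 of 32. Scaling the existing count over all active subjects is simpler but detects less. The sponsor and DSMB should agree the final thresholds. Do not carry the flat count of 3 through 48.

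(b) Use one consequence in 3.1, 9.1, 9.2 and 12.9: when a criterion is met, suspend the cohort and escalation and convene the DSMB. If any contributing event is a related Grade 3+ toxicity, the stop on both is final. Otherwise the DSMB decides, and records, whether enrolment may resume and whether escalation may resume. Deleting the resume sentence from 3.1 and 9.2 would also remove the ambiguity.

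The cost is amendment text in four sections, possible extra DSMB time, and a 2% (scaled) to 4% (combination-arm) chance of an unneeded pause at a true rate of 5%. No extra patients are needed.
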